Title of Project: Glycemic Variability in Subclinical Lipohypertrophy

Principle Investigator: [name]
Title(s): MD, FRCP
Department: UBC Department of Medicine

Co-investigators:

1) [name]	UBC Department of Medicine
2) [name]	UBC Department of Medicine

Study: Ultrasound detection of lipohypertrophy in patients with diabetes mellitus

Purpose: To determine if subclinical lipohypertrophy affects insulin absorption and glycemic parameters in patients with lipohypertrophy.

Hypothesis: Early hypertrophic changes in the composition of the subcutaneous layer of adipose tissue may be detectable via ultrasound and could alter insulin absorption.

Objectives: To determine the effect of subclinical lipohypertrophy on glycemic variability

Background:

Lipohypertrophy is a well-documented phenomenon in patients with diabetes in which hypertrophy and differentiation of adipocytes occurs in the dermal reticular layer at sites of subcutaneous insulin injection(1). Historically, lipohypertrophy was more common in type 1 diabetes prior to the development of purified recombinant human insulin, however it has been documented as a complication of newer insulin analogs in both type 1 and type 2 diabetes (2-4). Areas of hypertrophic nodules have decreased vascularity and are associated with poor glycemic control resulting in higher insulin requirements when used as a site of insulin administration (5). Conversely, if the site of injection is changed where insulin dosing has been increased, there is a risk of significant hypoglycemia as absorption can vary at non-hypertrophic sites (5-7). The detection of early, non-palpable lipohypertrophy remains difficult in the clinical setting. Recent studies have identified distinct ultrasonographic features of hyperechogenicity in areas of adipose tissue consistent with clinical evidence of lipohypertrophy at injection sites, and have detected changes in the thickness of subcutaneous tissue where not clinically evident in a population of patients with type 1 diabetes (8-10). Evaluation of insulin absorption at sites affected by clinically apparent lipohypertrophy through short-term continuous glucose monitoring has shown inconsistent results and it is yet unknown how or if subclinical lipohypertrophy affects absorption (11). In this study we propose to enroll at least 20 people who participated in phase 1 and who were determined to have subclinical lipohypertrophy to examine the correlation between

glycemic control and amount of insulin injected in subclinical hypertrophic areas using capillary blood glucose and continuous glucose monitoring.

Design, Specification of Endpoints, and Procedures:

Inclusion Criteria:

- **Participated in phase 1**
- **Determined to have subclinical lipohypertrophy**
- **Have had type 1 or type 2 diabetes for at least 2 years**
- **Currently using insulin to manage diabetes**
- **Have used insulin to manage diabetes for at least 2 years**
- **Age 19 or older**

Exclusion Criteria:

- **Taking insulin secretagogues (gliclazide, glyburide, glipizide) or other injectable medications (i.e. liraglutide/Victoza)**
- **Taking systemic steroids (e.g. prednisone)**
- **Not fluent in speaking and writing English (unless accompanied by a translator)**

In this second phase of the study, a minimum of 20 patients identified with subclinical lipohypertrophy in Phase 1 will be offered enrollment to assess glycemic correlation with injection in areas of subclinical lipohypertrophy. A separate enrollment and consent process will be undertaken by the diabetes nurse for this phase. Demographic information will be reviewed.

Patients will be randomized and data interpreters will be blinded to two alternating six-day protocols where the patients will be advised verbally and by written instruction to inject insulin in sites of subclinical lipohypertrophy or normal subcutaneous tissue. Patients will be asked to monitor and record their capillary blood glucose with meals and prior to bedtime using their own capillary blood glucose monitor. A trained research nurse at the Diabetes Centre will instrument each patient with an iPro 2 glucose sensor (Medtronic Canada). These sensors continuously measure blood glucose for periods of up to 7 days. A trained nurse will clean the skin with a superficial disinfectant and a small catheter will be inserted in the subcutaneous tissue at a non-lipohypertrophic site. The catheter will then be attached to a glucose sensor. Patients will wear this sensor for two periods of 6 days each at different sites. At the end of each of the two six day periods, the sensor will be removed.

Statistical Analysis:

In this phase of the study, we will measure the coefficient of variation of blood glucose during the different injection protocols. A student's paired t-test will be used to determine the difference if any in CV of glucose between injection sites.

Potential benefits:

Information gained from this study will expand the knowledge of the incidence of early hypertrophic changes, the ability to detect these changes using a novel ultrasound technique and the impact of these changes on glycemic control with insulin. Patients found to have hypertrophic changes will be advised to inject insulin at alternate sites and will be re-educated on the importance of injection site rotation. Patients with poor glycemic control may be able to improve their glycemic parameters or reduce their insulin dose should their requirements be due to insulin absorption issues at hypertrophic sites.

Risks:

There may be some discomfort associated with the insertion of the glucose sensor. There is a small risk of skin infection from the insertion of the glucose sensor and catheter and the possibility of an allergic reaction from the tape used to apply it. This risk occurs less than 1 in 1000 times the sensor is used. If patients have concerns regarding insulin dose adjustments they will have access to a diabetes education and research nurse who can assist with insulin dose titration. Any additional adverse events will be monitored by a trained research nurse at the Diabetes Centre.

References:

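### The randomised two-period comparison is analysed by a plain paired t-test with no period term; a blocked order and a 2x2 crossover analysis would protect power at almost no cost

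*Combined protocol and SAP*

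**What the plan says.** Under Design, Specification of Endpoints, and Procedures, the combined protocol and SAP states: "Patients will be randomized and data interpreters will be blinded to two alternating six-day protocols". The same section adds: "Patients will wear this sensor for two periods of 6 days each at different sites". So each patient contributes one period under each injection protocol. Order is the natural reading of what is randomised, although the text never says so outright. It gives no allocation ratio, no blocking and no method for generating the list.

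On size, "a minimum of 20 patients identified with subclinical lipohypertrophy in Phase 1 will be offered enrollment", with no calculation behind the number.

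Under Statistical Analysis, the endpoint is set by "we will measure the coefficient of variation of blood glucose during the different injection protocols" and the method by "A student's paired t-test will be used to determine the difference if any in CV of glucose between injection sites". No period or sequence term appears anywhere. The plan also states no alpha, sidedness, power, expected difference or SD of the within-patient difference.

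**The concern.** Two protocols given in two successive periods in random order make a 2x2 crossover. If mean CV differs between the first and second period for reasons unrelated to injection site, a plain paired t-test handles this badly in two ways. The shift raises differences in one order and lowers them in the other, so it inflates the residual variance. If the orders are unequal in size, part of the shift also carries into the estimated site difference.

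The plan documents no such shift but leaves room for one. Each period has its own sensor placement, patients check and record their glucose throughout, and under Risks "they will have access to a diabetes education and research nurse who can assist with insulin dose titration". With a minimum of about 20 patients, avoidable residual variance matters. The randomised order already holds the information needed to remove it.

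**Working it through.** **Inputs from the document.** At least 20 patients, two periods each, a paired t-test on CV. The number 20 cannot be reproduced, because no effect, SD, alpha or power is given.

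**Assumed inputs.** n = 20 analysed; alpha 0.05, two-sided; site effect d = 0.66 SD of the paired difference, which is simply the effect that gives about 80% power at n = 20 with no period effect; period shift P (mean of period 1 minus period 2) from 0 to 1.0 in the same SD units.

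**Model.** For each patient let D be CV at lipohypertrophic sites minus CV at normal sites. Then

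D = d + P·s + e, with s = +1 if the lipohypertrophic sites come first, s = −1 otherwise, and e ~ N(0,1).

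Let n1 and n2 be the numbers in the two orders.

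**Paired t-test, 19 df, critical t 2.093.**
- Given the split, the mean of D is centred at d + P(n1 − n2)/n. At 13/7 the displacement is (6/20)P = 0.3P; at 10/10 it is zero.
- The sum of squares is noncentral chi-square on 19 df with noncentrality 4·n1·n2·P²/n. At 10/10 this is 20P², so the expected variance is 1 + (20/19)P². At P = 1.0 the SD is inflated by √(1 + 20/19) = 1.43.

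**Crossover analysis, 18 df, critical t 2.101.**
- Estimate: the average of the two order-specific means of D. P cancels at any split.
- SE = ½√(1/n1 + 1/n2). At 10/10 this is ½√0.2 = 0.2236 = 1/√20, the same as for the paired test. Only one degree of freedom is lost.

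**Power at d = 0.66** (numerical integration for the paired test, noncentral t for the adjusted test)

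| P (SD) | Paired, 10/10 | Adjusted, 10/10 | Paired, simple randomisation | Adjusted, simple randomisation |
|---|---|---|---|---|
| 0 | 0.799 | 0.797 | 0.799 | 0.775 |
| 0.25 | 0.781 | 0.797 | 0.775 | 0.775 |
| 0.5 | 0.722 | 0.797 | 0.707 | 0.775 |
| 1.0 | 0.494 | 0.797 | 0.501 | 0.775 |

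The simple-randomisation columns average over Binomial(20, 0.5) splits. Adjustment has the higher power once P exceeds 0.09 SD with a 10/10 split, or 0.25 SD under simple randomisation.

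**Mean 95% CI width at 10/10.** Paired: 0.95, 1.04 and 1.33 SD at P = 0.25, 0.5 and 1.0. Adjusted: 0.93 SD throughout.

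**Type I error of the paired test, given the split**

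| Split | P = 0.25 | P = 0.5 | P = 1.0 |
|---|---|---|---|
| 10/10 | 0.044 | 0.029 | 0.006 |
| 12/8 | 0.049 | 0.045 | 0.030 |
| 13/7 | 0.055 | 0.066 | 0.075 |
| 14/6 | 0.064 | 0.097 | 0.165 |
| Average, simple randomisation | 0.050 | 0.050 | 0.051 |

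The paired test is conservative up to 12/8 and anti-conservative from 13/7 outward. Under simple randomisation a split of 13/7 or worse has probability 0.263. The adjusted test holds 0.05 at every split. Simulation agrees with these figures.

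**The case against.** The strongest reply is that the plan contains no error. A paired t-test on a randomised two-period comparison has zero mean bias and about 5% type I error over the randomisation. That is correct, and it limits the point to efficiency and to behaviour given the split actually obtained.

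The benefit also depends on a period shift that the document neither states nor bounds. Nurse-assisted titration is on request, so it need not produce a shift common to all patients. P = 1.0 SD is about 1.5 times the assumed site effect and should be read as an extreme. At P = 0.25 SD and 10/10 the gain is only 1.6 points (0.797 − 0.781). All of this stands. It argues for modest expectations, not against a change that costs almost nothing.

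The cost is one degree of freedom only if the patients analysed are balanced by order. Blocking balances those randomised, not those who complete. With no period effect, adjusted against paired power is 0.773 against 0.777 for completers of 10/9, 0.743 against 0.752 for 10/8, 0.707 against 0.724 for 10/7, and 0.662 against 0.694 for 10/6. This qualification stands; the extra cost is small unless dropout is heavy and one-sided.

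Finally, the order may already be blocked, since the plan is silent. In that case only the analysis sentence needs to change, and the unadjusted test would be needlessly conservative whenever P is not zero.

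**Conclusion.** The point holds as an inexpensive improvement. With balanced order, adding period changes power by −0.2 points if there is no period effect. It gains 1.6 points at a shift of 0.25 SD, 7.5 at 0.5 SD (0.797 − 0.722) and about 30 at 1.0 SD (0.797 − 0.494). It also keeps type I error at 5% whatever split is realised. The planned test remains valid on average over the randomisation.

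The absolute power figures are illustrative, because alpha, sidedness, the 0.66 SD effect and the range of P are all assumed. The conclusion also rests on reading the randomisation as one of order. A period term does not address carryover between the two periods.

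**What to change.** Make two changes together.

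1. State that order is randomised 1:1 in permuted blocks, so that the two sequences are equal in size, and describe how the list is generated and kept from the enrolling nurse.
2. Replace the paired t-test sentence with the 2x2 crossover analysis: a mixed model for CV with injection site, period and sequence as fixed effects and patient as random effect, or the two-sample comparison of period differences between sequences. The two agree when every patient supplies both periods. Name one as primary, say how a patient with one missing period is handled and, for the mixed model, which degrees-of-freedom method applies. Report the site difference with its 95% CI, and fix the wording before unblinding.

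The cost is a blocked list and a few lines of text; no extra data are needed. Adjusting without blocking is a poorer bargain. With no period effect it loses about 2.5 points of power on average under simple randomisation (0.775 against 0.799) and about 4 points at 13/7 (0.759 against 0.799).

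### Risks does not name low glucose on moving to normal injection sites, and an analysis of CV alone cannot show whether glucose is lower there

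*Combined protocol and SAP*

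**What the plan says.** **Risk of changing site.** The Background states that "if the site of injection is changed where insulin dosing has been increased, there is a risk of significant hypoglycemia". It also says of the population studied here that "it is yet unknown how or if subclinical lipohypertrophy affects absorption".

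**Intervention.** Under Design, Specification of Endpoints, and Procedures, patients are randomized to two alternating six-day protocols in which "the patients will be advised verbally and by written instruction to inject insulin in sites of subclinical lipohypertrophy or normal subcutaneous tissue". The supplied text gives no rule for the insulin dose at the switch. On monitoring, "Patients will be asked to monitor and record their capillary blood glucose with meals and prior to bedtime", and a continuous sensor is worn in both periods.

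**Risks.** The section begins "There may be some discomfort associated with the insertion of the glucose sensor", then names skin infection and allergy to the tape. It offers nurse help with dosing to patients who have concerns, and says a research nurse will monitor any other adverse events. Hypoglycemia is not mentioned.

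**Aims and analysis.** The Purpose is "To determine if subclinical lipohypertrophy affects insulin absorption and glycemic parameters in patients with lipohypertrophy". The Objective is narrower: "To determine the effect of subclinical lipohypertrophy on glycemic variability". The whole inferential plan is: "A student's paired t-test will be used to determine the difference if any in CV of glucose between injection sites".

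**The concern.** There are two linked gaps.

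First, every named risk belongs to the measuring device and none to the intervention. A patient whose dose had been raised while injecting into affected tissue could have low glucose after moving to normal tissue at the same dose. The protocol recognises this mechanism in its Background. Under Potential benefits it also counts a possible dose reduction as a gain. The matching hazard, too much insulin effect at an unchanged dose, is not listed.

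Second, CV is SD divided by mean. It measures relative spread and carries no information on level. If insulin is better absorbed from normal tissue, the most direct consequence is lower glucose, and the planned test cannot show it. Capillary checks and adverse-event monitoring may catch individual lows, but no comparison of glucose level or of lows between sites is planned. The absorption and glycemic-parameter part of the Purpose would go unanswered even though the data to address it are collected.

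**Working it through.** **Inputs.** From the documents: at least 20 patients, two six-day periods each, paired t-test on CV. The documents give no glucose level, CV, SD, event rate or hypoglycemia threshold, so there is no figure of the plan's own to reproduce. Everything numerical below is an illustration. Assumed: mean 9.0 mmol/L, CV 36% (SD 3.24), threshold 4.0 mmol/L, and falls of 10% or 20% at normal sites.

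**1. CV does not identify level (algebra only).** If all glucose values are multiplied by k, SD and mean both scale by k, so CV(kG) = kSD/(k·mean) = CV(G). A proportional fall of any size leaves CV unchanged. If instead SD stays fixed and the mean falls 20%, CV = 3.24/7.2 = 45%. That rise looks the same as greater variability at an unchanged mean.

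**2. Time below 4.0 mmol/L with CV held at 36%.**
- Lognormal: σ = √ln(1 + 0.36²) = 0.349; μ = ln(mean) − σ²/2; P = Φ((ln 4 − μ)/σ).
- Normal: P = Φ((4 − mean)/(0.36 × mean)). For mean 9.0, z = −1.543; for mean 7.2, z = −1.235.

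| Mean (mmol/L) | CV | Lognormal | Normal |
|---|---|---|---|
| 9.0 (no fall) | 36% | 1.58% | 6.14% |
| 8.1 (10% fall) | 36% | 3.24% | 7.99% |
| 7.2 (20% fall) | 36% | 6.56% | 10.85% |

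For a 20% fall the rise is 6.56 − 1.58 = 4.98 points (4.1-fold) or 10.85 − 6.14 = 4.71 points (1.8-fold). For a 10% fall the ratios are 2.0 and 1.3.

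**3. Sensitivity.** Over means of 8, 9 and 10 mmol/L and CVs of 30%, 36% and 40%, the ratio for a 20% fall runs from 2.8 to 9.1 (lognormal) or 1.6 to 2.2 (normal). The relative size depends heavily on the assumed distribution.

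**4. Dose corrected after 2 of the 6 days.** One third of the period is at mean 7.2 and two thirds at 9.0.
- Mean = (7.2 + 2 × 9.0)/3 = 8.4.
- Second moment = 1.1296 × (51.84 + 2 × 81)/3 = 80.52, where 1.1296 = 1 + 0.36².
- SD = √(80.52 − 8.4²) = √9.96 = 3.156; CV = 3.156/8.4 = 37.6%.
- Time low = (6.56 + 2 × 1.58)/3 = 3.24% (lognormal) or (10.85 + 2 × 6.14)/3 = 7.71% (normal), a rise of about 1.6 to 1.7 points.

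CV moves by only 1.6 points and still gives no direction.

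**5. What 20 pairs can estimate.** The 95% half-width is t(0.975, 19) × SD/√20, with t = 2.093 and SD that of the paired differences (assumed).
- Mean glucose: SD 2 gives ±0.94 mmol/L (SD 1: ±0.47; SD 3: ±1.40), against illustrated falls of 1.8 (20%) and 0.9 (10%).
- Time low: SD 5 points gives ±2.34 points (SD 3: ±1.40; SD 10: ±4.68).

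At SD 2 mmol/L, a paired t-test at two-sided 5% has about 97% power for a fall of 1.8 and about 48% for 0.9.

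**The case against.** **The safety half is conditional.** The Background warning applies where doses have been raised, and it follows text on hypertrophic nodules, whereas this trial enrols subclinical disease. No document says how many patients have a raised dose. This stands, and it limits the claim to a possible risk. It does not justify silence, because the added sentence can state both conditions.

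**Safeguards may exist elsewhere.** Consent pages were removed from the supplied text and the written injection instruction is not supplied, so either may name hypoglycemia or give a dose rule. Nurse help, adverse-event monitoring and capillary checks are visible. This also stands: the point concerns the Risks section only, and the visible cover is partial. Nurse help depends on the patient raising a concern, and no threshold or action is attached to the capillary readings.

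**Moving to normal tissue is also ordinary advice.** Under Potential benefits, patients with hypertrophic changes are told to use other sites, so the risk is not created by the trial alone and some patients may already have moved. That is fair, but the trial still directs site use over set periods, and the text does not say when the advice is given.

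**CV matches the title and the Objective, and the mean must be computed to obtain it.** This is correct and is why CV should stay primary. But computing a mean is not the same as planning to compare it, and the Purpose is wider than the Objective. The Background also speaks of glycemic control and the amount of insulin injected.

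**The remedy is imprecise.** Power for a 10% fall is about 48% at SD 2 mmol/L and about 25% at SD 3. A time-low rise of 1.6 to 1.7 points lies inside ±2.3. Dose changes also affect mean glucose, and logging their dates does not remove that effect. These limits are real, so the results should be reported as estimates.

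**Conclusion.** Both halves hold. The omission from Risks is a matter of text: the protocol describes a hazard of changing site, makes directed site use its intervention, and lists only sensor harms. How often the hazard would occur here cannot be said, since the effect of subclinical disease on absorption is unknown and raised doses are not documented.

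The analysis gap follows from the definition of CV and needs no assumed value. The illustrated size, about 5 more percentage points of time below 4.0 mmol/L for an uncorrected 20% proportional fall with no change in CV, rests wholly on the assumed mean, CV, threshold, fall and distribution. It is not a forecast for this trial. The CV comparison remains valid for the Objective; what it cannot do is answer the rest of the Purpose. This should be fixed, with medium confidence.

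**What to change.** 1. **Risks.** Add a sentence such as: Patients whose insulin dose has been raised may have low blood glucose when they move to normal injection sites; whether this happens with subclinical changes is not known. Record hypoglycemia as an adverse event with the injection period in which it occurred. Check that the consent form and written instruction agree. The clinical response to a low reading is for the investigators to define.

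2. **Statistical Analysis.** Keep CV as primary. Add two secondary within-patient differences (normal minus affected site) from the sensor data: mean glucose, and percent time below a threshold the investigators set in advance. Report each with a 95% confidence interval, using a signed-rank test if the differences are skewed.

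3. **Dose changes.** Log every insulin dose change with its date, so that a fall corrected by titration is not read as no difference.

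**Cost.** One sentence, a consent check, one adverse-event item, a dose-change note and two summaries of data already collected; no extra visits or procedures. The downside is limited precision with 20 patients, so the secondary results should be presented as estimates and not as proof of safety.
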